Study Title: Functional Resistance Training to Improve Knee Function after ACL Reconstruction

NCT Number: NCT03282565

Date: August 13, 2018

The objective of this study is to perform a pilot **randomized clinical trial** that assesses whether progressive functional resistance training during gait will significantly improve quadriceps function, neural excitability, and knee mechanics after ACL reconstruction. We anticipate that this approach will lead to symmetrical quadriceps strength and gait climbing biomechanics, complete voluntary activation, and improved neural excitability and patient-based outcomes.

Aim 1: Determine the effects of progressive functional resistance training during walking on knee outcomes after ACL reconstruction.

Hypothesis 1: Progressive functional resistance training while walking will result in greater improvements in knee extensor strength (primary outcome) than dose-matched treadmill walking. **Hypothesis 1B:** Voluntary activation, sagittal plane knee biomechanics and patient-reported outcomes will also be significantly better after progressive functional resistance training than after dose-matched treadmill training.

Aim 2: Determine the effects of progressive functional resistance training during gait on cortical and spinal reflex excitability of individuals with ACL reconstruction.

Hypothesis 2A: Progressive functional resistance training while walking will result in greater changes in corticospinal excitability than dose-matched treadmill walking. **Hypothesis 2B:** There will be a strong association between changes in knee extensor strength, voluntary activation and corticospinal plasticity.

APPROACH

Study Design for ACLR subjects: This is a single-center randomized controlled pilot trial of functional resistance training during treadmill walking. Patients with ACLR will be randomized using permuted blocks into one of three groups: 1) functional resistance training with a custom brace during treadmill walking, 2) functional resistance training with elastic bands during treadmill walking, and 3) treadmill walking (sham/control arm). Isometric quadriceps strength symmetry index will be our primary outcome measure. Our secondary outcome measures are: 1) % voluntary activation, 2) knee flexion angle symmetry, 3) knee moment symmetry. Our tertiary outcomes are: 1) patient-reported outcomes via Knee Injury and Osteoarthritis Outcome Score, 2) cortical excitability, and 3) spinal reflex excitability. All outcome measures will be examined at 3 study time points: 1) *Pre-intervention*: about 6 weeks after ACLR (a time-point when adequate quadriceps control is usually achieved), 2) *Post-intervention*: immediately after the intervention, and 3) *Follow-up*: 6-12 months post-ACLR (± 2 weeks) (when patients are typically cleared for return to activity) (Fig. 1).

Subject Characteristics: To be eligible for inclusion in the study, ACL subjects must meet the following criteria: 1) aged 14-40 years; 2) suffered an acute, complete ACL rupture; 3) scheduled to undergo ACL reconstruction with an autograft, 4) willingness to participate in testing and follow-up as outlined in the protocol; and 5) English-speaking. Exclusion criteria for the trial are: 1) inability to provide written informed consent; 2) female subjects who are pregnant or are planning to become pregnant (determined via self report); 3) previous ACL injury; 4) previous surgery to either knee; 5) recent significant knee injury; 6) history of uncontrolled diabetes or hypertension, and 7) patients who are contraindicated for TMS (e.g., metal implants in head, unexplained recurrent headaches, history of seizures, epileptogenic drugs, active psychiatric illness, etc.). To be eligible for inclusion in the study, healthy subjects must meet the following criteria: 1) aged 14-40 years; 2) have no history of major knee injury, 3) willingness to participate in testing and follow-up as outlined in the protocol; and 4) English-speaking. Exclusion criteria for healthy subjects are: 1) inability to provide written informed consent; 2) female subjects who are pregnant or are planning to become pregnant (determined via self report); 3) previous ACL injury; 4) previous surgery to either knee; 5) previous history of significant knee injury; 6) history of uncontrolled diabetes or hypertension, and 7) patients who are contraindicated for TMS (e.g., metal implants in head, unexplained recurrent headaches, history of seizures, epileptogenic drugs, active psychiatric illness, etc.).

ACL Standard of Care Rehabilitation: Participants in all groups will undergo standard ACL rehabilitation (e.g., standard of care). Total standardization of the ACL rehabilitation program will not be possible given that the various concomitant injuries accompanying the ACL rupture may dictate a slower progression through exercises (e.g., patients with a meniscal repair will be progressed through rehabilitation slower than those with a meniscectomy). We have shown previously that meniscal treatment does not influence quadriceps function at the time of return to activity.¹ Further, the intervention of interest, functional resistance training, is being studied as an adjunct to the standard of care and is meant to supplement current practices. To ensure similar practices between therapists, we will have basic guidelines that therapists will follow.²⁻⁴ Further, to help ensure fidelity of the standard of care across patients, only 2 physical therapists, with a minimum of 5 years of experience, will deliver the rehabilitation. Additionally, guidelines will be discussed prior to the study initiation and a manual of operating procedures will be provided.

Study Interventions – ACL subjects

Functional Resistance Training: Patients randomized into this group will receive progressive functional resistance training while walking on a treadmill using a resistive device applied to the leg (resistance during walking could be applied via a resistive brace (using eddy current braking) or elastic tubing or cuff that is attached to the subject's leg). Subjects will exercise 2-3 ×/week for 8 weeks, beginning at ~6 weeks post-ACLR. To perform the exercise, patients will wear a brace/cuff/band that is capable of providing scalable resistive torques with their ACLR knee with range of motion limited to 10° to 70° of knee flexion. Patients will warm-up for 2 minutes by wearing the brace/cuff/band on the ACLR limb and walk on a treadmill at their comfortable walking speed with resistance set at zero level. Following the warm-up trial, each participant will perform six blocks of treadmill walking at their self-selected pace, with each block of training lasting for 5 minutes. Two minutes of rest will be provided after each block of training. Real-time kinematic feedback will be provided to ensure that subjects maintain proper kinematic patterns during the training.⁵⁻⁸ During resisted walking trials, subjects will cyclically engage their quadriceps and their hamstring muscles with the ACLR limb. The patients will train at an intensity equal to corresponding to a difficulty level between 5-7 on the OMNI scale.

Treadmill Walking (sham condition): Participants randomized to the treadmill walking group will receive treadmill training 3x/week for 8-12 weeks beginning at 6 weeks post-ACLR. The treadmill walking group will utilize the same equipment and follow the same protocol as in the functional resistance training intervention, with the exception that the intensity of the resistive brace/cuff/band will be set with no resistance throughout the training.

Objective 1: Determine the effects of progressive functional resistance training during walking on knee outcomes after ACL reconstruction. The goal of Aim 1 is to test the hypothesis that functional resistance training during walking will improve knee outcomes to a greater extent than dose-matched treadmill walking in individuals with ACLR. Subjects with ACLR will participate in an 8-week training program. Knee outcomes will be assessed before, immediately after the intervention, and at 6 months after ACLR.

Knee Strength and Voluntary Activation: Quadriceps strength and voluntary activation will be measured at 60° of knee flexion with the interpolated triplet technique as we have done previously.^{1,9-12} This method provides detailed information about strength as well as the level to which a subject can activate the quadriceps muscle.^{11,13-15} Quadriceps strength symmetry index will be computed by normalizing peak torque of the reconstructed leg to that of the non-reconstructed leg. Voluntary activation will be computed as in Fig. 3. Intra- and Inter-session reliability for recording isometric quadriceps strength and voluntary activation are high (ICC range $\geq .92$).¹⁶⁻²² Isokinetic knee strength will also be assessed at the second post-intervention testing session (measurement 3, figure 1).

Biomechanics: Three-dimensional biomechanical data will be collected for the knee during walking (along a 4 m walkway) using a 12 camera motion capture system sampling at 240 Hz and synchronized with analog data (force) sampling at 1200 Hz. Subjects will walk at a standardized speed 1.1 m/sec ($\pm 5\%$) as speed during level walking is known to influence lower extremity biomechanics. Five trials will be collected for each task and data will be analyzed for both limbs. Lower limb joint rotations will be defined based on the 3D coordinates of 32 retroreflective markers, as we have done previously. A static trial of each participant aligned within the laboratory coordinate system will be recorded, allowing for a kinematic model composed of 7 skeletal segments. Rotations will be calculated using the Cardan rotation sequence²³ and will be expressed relative to each subject's neutral static position. Filtered kinematic data and ground reaction force data will then be submitted to a standard inverse dynamics approach. Joint moments will be normalized to subject's body height and mass. All biomechanical data will be time normalized to 100% of the stance phase for walking and stair descent, with initial contact and toe-off being defined using a vertical ground reaction force threshold of 10 N.^{24,25} We will use the symmetry values (i.e. (involved limb/uninvolved)×100) for the sagittal plane peak knee angles and moments recorded during weight-acceptance phase (initial contact to peak knee flexion) for walking and for stance during stair descent for analyses. The same, trained investigator will apply markers for all testing to minimize error. Good intra- (ICC $> .80$) and inter-session (ICC $> .90$) reliability has been established for sagittal plane biomechanics using 3D motion capture.

Patient-Reported Outcomes Measure: The Knee Injury and Osteoarthritis Outcome Score (KOOS) survey²⁶ will be used to obtain the subject's opinion about their knee and associated problems. KOOS is valid and reliable measure (ICC = .75-.93) for assessing the functional status and quality of life of athletes after ACLR.²⁷ We will also use the PROMIS, MARX scale, Tegner, and Tampa Scale for Kinesiophobia to quantify physical function, activity level (MARX and Tegner), and their fear of movement/activity, respectively.

Aim 2: Determine the effects of progressive functional resistance training during gait on cortical and spinal reflex excitability of individuals with ACL reconstruction. The goal of Aim 2 is to test the effects of progressive functional resistance training during walking on cortical and spinal reflex excitability in individuals with ACLR. Cortical and spinal excitability will be assessed before, immediately after the intervention, and at 6 months after ACLR. The assessor will be blinded to patients' group assignment.

Motor Cortical Excitability: Motor cortical excitability changes due to functional resistance training will be evaluated using reliable ($ICC \geq .82$) single- and paired-pulse TMS protocols similar to our prior studies. First, the optimal site for eliciting quadriceps MEP (i.e., hotspot) will be determined using a double cone TMS coil, which is specifically designed for stimulating the leg motor cortex. The hotspot will be identified by determining the stimulation location that produces largest and most consistent MEPs. A frameless stereotaxic coil tracking system will be used to assure consistent placement of the coil during the experiment.^{42,43} Active motor threshold will then be established during a slight background contraction (~5% MVIC) by determining the lowest stimulus intensity that elicits an $MEP > 100\mu V$ in at least 5 of 10 consecutive trials.⁴⁰ Recruitment curves will be created by measuring motor evoked potentials (MEPs) and evoked torque responses of the quadriceps muscle over a range of TMS intensities (70% to 140% AMT). The intervention-mediated changes in cortical excitability will be assessed by examining the changes in MEP/torque amplitudes and slopes of recruitment curves obtained using Boltzmann equation. In cases where sigmoidal relationship is not appropriate ($R^2 < 0.80$), other fits (e.g., linear) will be used as appropriate.

H-Reflex Testing: Spinal reflex excitability will be measured with H-reflex testing using a reliable intra- and inter-session protocol ($ICCs > 0.90$)⁵¹ that we have employed previously.^{52,53} Briefly, patients will be positioned supine with the knee supported in flexion and hands at their sides. Factors such as head position, hand movement, etc. may affect the H-reflex so care will be taken to minimize movement. H and M recruitment curves will be mapped for the ACLR limb by applying a 1ms square-wave stimulus to the femoral nerve and recorded using EMG. Stimuli will be delivered by increasing the intensity in 0.2V increments, with a 10-second rest interval after each stimulus until the maximum H-reflex and maximum M-wave are obtained. Three peak-to-peak amplitudes of the maximum H-reflex and M-wave will be recorded and used to create the H-reflex to M-wave ratio.

Analytic Plan: Descriptive statistics will be used to explore the distribution, central tendency, and variation of each measurement, with an emphasis on graphical methods. Normality for each variable will be checked using a Shapiro-Wilks test, and appropriate transformations (e.g., log) will be made when necessary. Linear mixed models will be used to compare the continuous primary and secondary endpoints between the experimental and control arm of the randomized group. Fixed-effects terms will include group, time, group \times time interaction, gender, group \times gender interaction, and other potential covariates such as, age, activity level, and meniscal repair. Patients will be included as random effects in the intercept. A significant main or interaction effect at $\alpha = 0.05$ will be followed by appropriate post-hoc analysis with adjustments for multiple comparisons.

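### The post-intervention visit is tied to the end of training, with no stated week after surgery and no rule for participants who stop early, so stage of recovery at that visit may differ between arms

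*Combined protocol and SAP*

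**What the plan says.** Study Design for ACLR subjects lists three assessments. The first is placed relative to surgery ("Pre-intervention*: about 6 weeks after ACLR"), and so is the third ("Follow-up*: 6-12 months post-ACLR (± 2 weeks"). The second is placed only relative to training ("Post-intervention*: immediately after the intervention"), with no week and no window. Objective 1 repeats this: "Knee outcomes will be assessed before, immediately after the intervention, and at 6 months after ACLR". Aim 2 gives the same timing for the excitability measures.

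The length of training is stated three times. For the resistance groups: "Subjects will exercise 2-3 ×/week for 8 weeks, beginning at ~6 weeks post-ACLR". The sham paragraph says that its participants "will receive treadmill training 3x/week for 8-12 weeks beginning at 6 weeks post-ACLR". Objective 1 then says of everyone: "Subjects with ACLR will participate in an 8-week training program".

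The Analytic Plan specifies a linear mixed model: "Fixed-effects terms will include group, time, group \times time interaction, gender, group \times gender interaction". Age, activity level and meniscal repair follow as examples of further covariates. Actual weeks since surgery is not listed. The text names no primary time point, no analysis population and no handling of missed visits. It does not say whether, or when, a participant who stops training is assessed.

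**The concern.** Under ACL Standard of Care Rehabilitation, every group receives standard rehabilitation throughout. Quadriceps symmetry can therefore be expected to change with time since surgery, whatever the randomised training does. A visit that moves with the end of training mixes the two. If mean time since surgery at visit 2 differs between arms, part of the group-by-time contrast is recovery time rather than resistance.

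There are three routes. Completers may be tested at different weeks because the stated durations differ by arm. Early stoppers, if tested when they stop, would contribute earlier values under the same visit label. Early stoppers who are not tested would leave a post value based on those who kept training, and tolerance may differ by arm because only the resistance groups train against load, at 5-7 on the OMNI scale. The routes need not push the result the same way, so they could not be separated afterwards without stop dates.

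**Working it through.** The plan gives no sample size, standard deviation, target effect, recovery rate or stopping rate, so it has no figure of its own to reproduce. The calendar arithmetic below uses the documents' figures. Everything after it uses assumed values and is illustrative.

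**1. Planned week of visit 2** = start week + training weeks.
- Resistance groups: 6 + 8 = about week 14.
- Sham, from its own paragraph: 6 + 8 = week 14 to 6 + 12 = week 18.
- Sham, from Objective 1: 6 + 8 = week 14.

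The possible gap among completers is therefore 0 to 4 weeks, with sham later.

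**2. Effect of a gap among completers.** Bias in (resistance minus sham) = −slope × gap. Assumed slope: 0.5 to 2 symmetry-index points per week.
- Mean gap 0 weeks: 0.
- Mean gap 2 weeks: −0.5 × 2 = −1 to −2 × 2 = −4 points.
- Mean gap 4 weeks (all sham participants train for 12 weeks): −0.5 × 4 = −2 to −2 × 4 = −8 points.

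**3. Early stoppers tested on stopping.** Bias = −slope × weeks early × (stop rate in resistance − stop rate in sham), with the same slopes and assumed stop rates.
- Equal rates and equal earliness: 0. Only noise is added. For 10-20% stopping 4 weeks early its SD is slope × 4 × √(p(1−p)), from 0.5 × 4 × √(0.1 × 0.9) = 0.6 to 2 × 4 × √(0.2 × 0.8) = 3.2 points.
- 20% against 10%, 4 weeks early: −0.2 to −0.8 points.
- 30% against 10%, 6 weeks early: −0.6 to −2.4 points.
- 10% against 20%, 6 weeks early: +0.3 to +1.2 points. The sign reverses.

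**4. Early stoppers not tested.** Suppose 20% stop in a resistance arm and 5% in sham, and stoppers would have scored 10-20 points below completers. The completer mean then exceeds the full-arm mean by 0.20 × 10 to 20 = 2 to 4 points (resistance) and 0.05 × 10 to 20 = 0.5 to 1 point (sham). The net is +1.5 to +3 points in favour of resistance, before whatever the mixed model recovers from baseline and covariates. If sham had more stoppers, this sign would reverse too.

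**5. With a common visit week.** The difference in mean test week is 0 by design, so the biases in steps 2 and 3 vanish for any slope or stop rate. The bias in step 4 shrinks only as far as stoppers actually attend.

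**The case against.** The strongest reply is that the intervention can fairly be read as the scheduled 8-week programme, since the Objective 1 sentence on timing follows directly on the one describing that programme. On that reading visit 2 falls at about week 14 whether or not someone stopped. Fig. 1, cited with the time points, may also show a week. A reader might infer that early stoppers will be tested too soon or not at all. The documents do not say so; they are silent, and testing on stopping, testing at the scheduled end and not testing are all open. This reply stands against the inference, but the text still gives no window or rule, and the sham paragraph's 8-12 weeks remains.

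A reader might also take visit 2 as the main comparison. No primary time point is named, and visit 3 is anchored to surgery, so its timing does not depend on when training ends.

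Slower progression after meniscal repair might be offered as a reason for early stopping. The documents tie it to standard rehabilitation, not to study training.

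Nor can it be presumed that the resistance arms would lose more people. As written, sham involves 3 × 8 = 24 to 3 × 12 = 36 sessions against 2 × 8 = 16 to 3 × 8 = 24, so its burden could be the higher one.

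Finally, testing at the end of exposure is a legitimate choice for a pilot of training effects. That is true, but it needs equal exposure lengths across arms, or a model that accounts for elapsed time. The text secures neither.

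**Conclusion.** The point holds as a design weakness that is cheap to remove. As written, time since surgery at visit 2 can vary with training duration, including by arm, and the model lists no term to account for it. The best-documented part is the completers' timing: about week 14 against weeks 14-18, a gap of 0 to 4 weeks that depends on which duration statement governs.

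The documents do not establish that the comparison is distorted. Timing bias from stopping needs stop rates or earliness to differ by arm, and selection bias needs missingness that is informative given the model. Neither can be judged from the text. Under the assumed rates and slopes, early stopping gives zero to a few index points in either direction, and a full 4-week gap among completers gives 2 to 8 points against resistance. With no standard deviation or target effect stated, none of these can be called large or small relative to the trial's aim.

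**What to change.** - Reconcile the three statements of training duration.
- Set visit 2 at one common number of weeks after the pre-intervention test (or after surgery), with one window for all three arms. If Fig. 1 already shows a week, bring it into the text.
- State that every randomised participant is asked to attend visits 2 and 3 whether or not training was completed, and that these values are analysed in the randomised arm.
- Record sessions completed and the date of and reason for stopping training.

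The cost is protocol wording and one short record. There are three drawbacks: some participants who pause training may be tested before they make up sessions, those who stopped must be asked back for a visit, and the estimate will include incomplete training and so may be slightly smaller.

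### The control arm is called dose-matched, but its written schedule allows more sessions and a later immediate post-test than the resistance arms

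*Combined protocol and SAP*

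**What the plan says.** Hypothesis 1 states that resistance training "will result in greater improvements in knee extensor strength (primary outcome) than dose-matched treadmill walking". Hypothesis 1B uses a dose-matched comparator too, and so does Hypothesis 2A: "will result in greater changes in corticospinal excitability than dose-matched treadmill walking". Objective 1 repeats it: resistance training "will improve knee outcomes to a greater extent than dose-matched treadmill walking in individuals with ACLR".

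The schedules are given by arm under Study Interventions – ACL subjects:

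- Functional Resistance Training: "Subjects will exercise 2-3 ×/week for 8 weeks, beginning at ~6 weeks post-ACLR".
- Treadmill Walking (sham condition): "Participants randomized to the treadmill walking group will receive treadmill training 3x/week for 8-12 weeks beginning at 6 weeks post-ACLR".

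Two other statements there bear on the schedule. The control arm will "follow the same protocol as in the functional resistance training intervention", and the only exception named is the absence of resistance. Objective 1 adds, without excepting any arm: "Subjects with ACLR will participate in an 8-week training program".

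On timing, Objective 1 says: "Knee outcomes will be assessed before, immediately after the intervention, and at 6 months after ACLR". Study Design for ACLR subjects likewise ties the second assessment to the end of training and the third to time since surgery. No primary time point is named for the quadriceps strength symmetry index.

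**The concern.** Two arm-specific schedules that differ in both weekly frequency and duration cannot easily be squared with a dose-matched comparator, a shared protocol and a single 8-week program. Staff could follow either set of statements in good faith, and the report could then claim dose-matching for arms that were not matched.

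The second consequence concerns timing. The post-intervention visit follows the last training session, so a control patient who trains beyond 8 weeks is tested later after surgery than a resistance patient. All arms continue standard rehabilitation throughout (ACL Standard of Care Rehabilitation). Extra recovery time before the test would therefore probably favour control and work against the trial's own hypothesis at that visit. The Analytic Plan models time as a study visit. Its named covariates include neither weeks since surgery nor sessions attended, so nothing stated would deal with a difference once it had arisen.

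**Working it through.** The plan gives no total session count to reproduce, so the check is arithmetic on its stated schedules.

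**Inputs**, all from Study Interventions – ACL subjects:

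- Resistance arms: 2-3 sessions a week for 8 weeks, from about week 6 after surgery.
- Control arm: 3 sessions a week for 8-12 weeks, from week 6.
- Each session: six blocks of 5 minutes, so 6 × 5 = 30 minutes of training walking. This leaves out the 2-minute warm-up and the rests. Including the warm-up gives 32 minutes and does not change any ratio.

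**Formulas**

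- Sessions = sessions per week × weeks.
- Walking minutes = sessions × 30.
- Post-test week = start week + weeks of training.

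**Reading 1: the arm schedules apply as written**

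| | Resistance | Control |
|---|---|---|
| Sessions | 2 × 8 = 16 to 3 × 8 = 24 | 3 × 8 = 24 to 3 × 12 = 36 |
| Minutes | 16 × 30 = 480 to 24 × 30 = 720 | 24 × 30 = 720 to 36 × 30 = 1,080 |
| Post-test week | 6 + 8 = 14 | 6 + 8 = 14 to 6 + 12 = 18 |

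- Ratio, control to resistance: 24/24 = 1.0 to 36/16 = 2.25. Comparing minimum with minimum or maximum with maximum gives 24/16 = 36/24 = 1.5.
- Excess in control: 24 − 24 = 0 to 36 − 16 = 20 sessions, or 0 to 20 × 30 = 600 minutes.
- Post-test delay in control: 14 − 14 = 0 to 18 − 14 = 4 weeks.

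The control minimum equals the resistance maximum. The arms match only if every resistance patient trains three times a week and every control patient stops at 8 weeks, and no rule requires either.

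**Reading 2: the 8-week sentence overrides the control duration**

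- Sessions: 16-24 against 24; ratio 24/24 = 1.0 to 24/16 = 1.5.
- Excess in control: 0 to 24 − 16 = 8 sessions, or 0 to 8 × 30 = 240 minutes.
- Post-test: about week 14 in both.

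**Reading 3: the same-protocol sentence covers the schedule as well**

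- Sessions: 16-24 in both, post-test about week 14 in both, no scheduled gap. This reading requires setting aside the control arm's own explicit schedule.

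**Follow-up visit.** It is timed from surgery, so its date does not move. The interval since training ended can still differ under Reading 1. Taking 6 months as 26 weeks (an assumption), it is 26 − 14 = 12 weeks for resistance and 26 − 18 = 8 to 12 weeks for control.

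**The case against.** The strongest reply is that the document as a whole leans towards matching. Dose-matching is stated repeatedly, the control paragraph names resistance as its only exception, and the 8-week sentence excepts no arm. Against these stands one sentence, whose range includes 8 weeks and which may be a drafting leftover. That explanation is plausible and the arms may well be matched in practice. It does not tell staff which sentence to follow, and under the 8-week reading the unequal frequency remains.

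The 2.25 ratio and the 20-session excess are extremes: they need control at its maximum and resistance at its minimum together. This stands, and 1.5 is the fairer like-for-like figure.

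Figure 1, to which Study Design refers for the time points, could not be read and may show a training length or post-test week. If so, it could indicate which reading was meant, but the conflict in the text would remain.

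The harm is inferred. The documents give no recovery curve between weeks 14 and 18 and do not say whether extra unresisted walking affects strength. If the bias runs as suggested, it is conservative for Hypothesis 1, and the main risk is a missed effect at one of two post-baseline visits in a pilot. All of this stands as a limit on how much can be claimed.

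The covariate list is open-ended, and adjusting for sessions attended, which arises after randomisation, could itself introduce bias. Under the first reading, time since surgery at the post-test would largely be determined by arm. This stands too: the remedy is to align the schedules, not to add covariates.

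Dose-matched could be meant per session. The plan does not say so, and the timing difference would remain.

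**Conclusion.** The concern holds. The control schedule conflicts with the dose-matched hypotheses, with the same-protocol statement and with the 8-week program. As written, control patients are scheduled for 24-36 sessions against 16-24, an excess of 0-20, with an immediate post-test 0-4 weeks later. The excess falls to 0-8 sessions with no delay if the 8-week sentence governs, and to nothing if the same-protocol sentence covers the schedule.

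Confidence is high for the contradiction and the arithmetic, which assume only that patients attend as scheduled and start at about week 6. The direction of bias, against resistance training at the immediate post-test, is probable and rests on continued recovery under standard rehabilitation. Its size on the symmetry index cannot be estimated from the documents. This should be fixed: it is a wrong statement about the main comparison, and it is cheap to correct.

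**What to change.** Amend the two schedule sentences so that all three arms have the same weekly frequency and an 8-week duration, replacing the control arm's 8-12 weeks. Keep the post-test immediately after training, and give it one common window for all arms. In the report, tabulate sessions attended and weeks since surgery at each test by arm. If the schedules are to stay different, remove the dose-matched claim from Hypotheses 1, 1B and 2A and from Objective 1.

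The cost is a wording amendment and one visit window, with no extra patients or procedures. Capping control at 8 weeks saves up to 36 − 24 = 12 sessions per control patient. If the common frequency is three a week, a resistance patient who would have trained twice a week attends 24 − 16 = 8 more sessions, which is within what the plan already allows.
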